1 STUDY SYNOPSIS

Sponsor / Sponsor- Investigator	[name], PhD Head of Research Group Upper Extremities and Hand Teaching, Research & Development [name] [contact] [contact]
Study Title	Translation and validation of the Shoulder Instability Return to Sports Index (SIRSI) and Tampa Scale of Kinesiophobia Shoulder Instability (TSK-SI) into German
Short Title / Study ID	OE-236 SIRSI TSK-SI Validation
Protocol Version and Date	Version 2 (dated 09/07/2024)
Study Registration	Clinicaltrials.gov SNCTP
Study Category and Rationale	Risk Category A
Background and Rationale	Return to Sports (RTS) is an important outcome measure after shoulder instability treatment. The concept of Return to Sport is multifactorial consisting of physical, psychological, and social/contextual factors in an interplay with sociodemographic and injury factors. The Shoulder Instability Return to Sport Index (SIRSI) measures psychological readiness to return to sports in the shoulder instability. Similarly the Tampa Scale for Kinesiophobia (TSK) has been invented to measure an excessive fear of movement due to painful injury in chronic low back pain. The Scale was then adapted to the shoulder instability cohort. However, both questionnaires are currently not available in German and therefore not scientifically available for a German speaking population,
Risk / Benefit	Risk / benefit assessment
Assessment Objective(s)	The aim of the project is to translate the Shoulder Instability Return to Sports Index (SIRSI) and Tampa Scale of Kinesiophobia Shoulder Instability (TSK-SI) into a German version and assess its validity in a Swiss-German population of patients with shoulder instability treated conservatively or surgically and planning to return to sports.
Endpoint(s)	Shoulder Instability Return to Sports Index (SIRSI) Tampa Scale of Kinesiophobia – Shoulder Instability (TSK-SI) Western Ontario Shoulder Instability Index (WOSI) Subjective Shoulder Value (SSV) Sport Subjective Shoulder Value (sSSV) Return to Sports Level
Study Design	single centre cross sectional confirmatory analysis to validate a patient reported outcome measure.

	Deciaration of Heisitiki, the 1011-00F, the FIRA as well as other locally relevant legal and

Version 02, 09 07 2024 8/21

regulatory requirements. A clinical trial covered by ClinO Chapter 4 may be conducted in accordance with other rules than ICH-GCP guidelines, provided that such rules are recognised in the specialty in question and the protection of participants and data quality and security are guaranteed (ClinO Art. 5, Abs 2). If the clinical trial is not conducted according to ICH-GCP guidelines, the paragraph above must be adapted accordingly.

2 BACKGROUND AND PROJECT RATIONALE

Return to Sports (RTS) is an important outcome measure after shoulder instability treatment (Abdul-Rassoul et al., 2019). While the definition of returning to sport is not clear (Doege et al., 2021), efforts have been made to provide consensus (Ardern et al., 2016). The concept of Return to Sport is multifactorial consisting of physical, psychological, and social/contextual factors in an interplay with sociodemographic and injury factors. Furthermore, different stages of RTS have been defined (Ardern et al., 2016). To take all factors into account, outcome measures like the ACL-RSI for anterior cruciate ligament ruptures have been invented (Webster et al., 2008). To provide such a measure for the shoulder instability cohort have adapted the ACL-RSI to a shoulder instability population and named it the Shoulder Instability Return to Sport Index (SIRSI) (Gerometta et al., 2018). Since then, this outcome has been frequently used to determine psychological readiness to RTS (Rossi et al., 2022). Despite an available German translation, published by a German insurance company (Return-to-Competition Schulter: Shoulder Instability-Return to Sport after Injury (SIRSI)-Skala (vbg.de), accessed 23.01.2024), the SIRSI is not scientifically available for a German speaking population, because this version has never been officially translated and validated. Similarly the Tampa Scale for Kinesiophobia (TSK) has been invented to measure an excessive fear of movement due to painful injury in chronic low back pain(Miller et al., 1991). The Scale was then adapted to the shoulder instability cohort(van Iersel et al., 2023). However, it is currently not available in German. Therefore, this project seeks to translate the SIRSI and TSK-SI into a German version and validate them in a German speaking population in Switzerland.

3 PROJECT OBJECTIVES AND DESIGN

3.1 Primary objective

The aim of the project is to translate the Shoulder Instability Return to Sports Index (SIRSI) and Tampa Scale for Kinesiophobia – Shoulder Instability (TSK-SI) into a German version and assess its validity in a Swiss-German population of patients with shoulder instability treated conservatively or surgically and planning to return to sports.

3.2 Primary endpoints

The primary outcomes of interest are the SIRSI and the TSK-SI. The SIRSI has been adapted to the shoulder instability cohort from the Anterior Cruciate Ligament Return to Sport Index (ACL-RSI) by (Gerometta et al., 2018). It is composed of twelve items that are rated on a zero to ten. The single total score is calculated by multiplying the sum of each item and dividing it by 120. The worst score then is zero indicating no psychological readiness to RTS and 100 the best, indicating full psychological readiness to RTS. The TSK-SI is composed of 18 questions scored on a 4 point Likert-Scale from "Strongly agree" to "Strongly disagree". The lowest score is 18, indicating no kinesiophobia and 72, indicating

highest level of kinesiophobia. The outcomes will be assessed electronically between three months and two years after surgery or instability event.

3.3 Secondary endpoints

As a secondary outcome the Western Ontario Shoulderinstability Index (WOSI) was developed by Kirkley (2003) and is the most prominent PROM in clinic and research for shoulder instability. The WOSI consists of 21 items and four domains: Physical symptoms (10 items), Sports, recreation, and work (4 items), lifestyle (4 items) and emotions (3 items). The scale for each item ranges from 0 to 100, allowing for a total score of 0 (best) to 2100 (worst). A transformed value ranging from 0 to 100 may be calculated by dividing the total score by 21 and subtracting it from 100. This allows for the common scale of 0 (worst) to 100 (best).

The subjective shoulder value (SSV) was introduced by Gilbart and Gerber (2007) and provides a simple measure to represent shoulder functionality during activities of daily living (ADL). The patients are asked " "What is the overall percent value of your shoulder if a completely normal shoulder represents 100%?" if difficulties emerge with estimating a percentage another possibility is to ask "A completely normal shoulder would cost you €1000. How much would you be willing to pay for yours?" (Gilbart & Gerber, 2007). Because the standard SSV might lack sport specific context Descamps et al (2023) suggested the sport subjective shoulder value (sSSV) with the question "Regarding sports practice, what is the overall percent value of your shoulder, if a completely normal shoulder represents 100% and a non-functional shoulder represents 0%?". Both scales result in a value between zero and 100, where zero means no subjective functionality during ADL or Sport respectively (Descamps et al., 2023).

Ardern et al (2016) defined *RTS* as that the athlete has returned to his previous sport but not necessarily at the same performance level and differentiated it to *return to participation* and *return to performance*. This spectrum will be assessed using custom build questions to determine the RTS level (Ardern et al., 2016).

3.4 Study Design

This study is a single centre cross sectional confirmatory analysis to validate two patient reported outcome measures.

4 PROJECT POPULATION AND STUDY PROCEDURES

4.1 Project population

The targeted population to sample from comprises patients with conservative or operative treatment of anterior shoulder instability, who wish to return to sports after a shoulder instability event.

An instability event is defined as a complete dislocation of the glenohumeral joint that needs to be repositioned by a health care professional or repositioned itself spontaneously, or a subluxation where the shoulder almost dislocates however not completely. Not an instability event are voluntarily dislocations or subluxations that can be provoked by the patient.

4.2 Inclusion criteria

Patients are included if they had a shoulder instability event within last year, where an instability event is defined as a) a complete dislocation of the glenohumeral joint that had to be reduced by a clinician or reduced itself spontaneously or b) a subluxation that suddenly almost dislocated but not completely. Dislocations or subluxations that can be induced by patients voluntarily are not considered an instability event. Patients must be above the age of 18 years. Furthermore, they must have signed a general consent for the use of data in scope of the local shoulder instability register at the Schulthess Klinik Zürich.

4.3 Exclusion criteria

Patients are excluded if they are not at least three months after the last instability event or a surgery for shoulder instability, if they do not endeavor to return to their sport, have another physical or psychological disorder not related to shoulder instability that compromises return to sport, have a language barrier to complete the questionnaires in German or are legally incapable of participating in this study.

Table 1: Overview over the inclusion and exclusion Criteria

Inclusion Criteria	Exclusion Criteria
1. Had an instability event within last year	1. Are at least three months after surgery or
2. Provided general consent for local shoulder	instability event
instability register	2. Must endeavor to return to their sport
3. Adult patients aged 18 or older	3. Have another physical or psychological disorder not related to shoulder instability compromising return to sports
	4. Have a language barrier to complete the questionnaires in German
	5. Are legally incapable of participating in research studies

4.4 Sample Size

According to the estimates that Gerometta et al (2018) provided in their validation study on the development of the SIRSI, the sample size to detect a Cronbach's alpha of 0.96 with a 95%-CI width of 0.1 is 9 patients. To detect a Pearson correlation coefficient of 0.71 with a CI-width of 0.2 a sample size of 99 is warranted and to detect a difference in means of 22.8 with a CI-width of 20 a sample size of 117 is necessary. To account for a dropout rate of 15% in this cohort a final sample size of 135 is needed to perform the below-mentioned analysis with a satisfying precision. As the TSK-SI is relatively new, no data is available to estimate the mean and standard deviations of the TSK-SI. Therefore, to validate the TSK-SI the sample size calculated for the SIRSI is considered sufficient. Sample size calculations have been conducted with the help of the presize package (Haynes et al., 2021) and the congruent web based application (https://shiny.ctu.unibe.ch/presize/, accessed on 03.04.2023).

sample size for Cronbach's alpha calpha k n conf.width conf.level lwr upr

1 0.96 12 9 0.1 0.95 0.88588 0.9892657

```
sample size for pearson 's correlation coefficient
r n conf.width conf.level lwr upr
1 0.71 99 0.2 0.95 0.5961453 0.7958619
```

```
sample size for mean difference with equal variance
delta sd1 sd2 n1 n2 conf.width conf.level lwr upr
1 22.8 26.6 26.6 71.82715 45.2511 20 0.95 12.8 32.8
```

4.5 Recruitment, screening and informed consent procedure

The recruiting takes place at the Schulthess Klinik Zürich. Patients who provided consent for the further use of health-related personal data for research purposes and were included in the local shoulder instability registry (SIR) (BASEC: 2020-01091), are screened for the inclusion criteria 1, 2 and 3.

Those patients will be contacted by email. In the email the study purpose, inclusion- and exclusion criteria are explained and a link to the eCRF is provided, as well as a study information attached. Furthermore, it is explained, that filling out the eCRF is considered as an agreement to participate in this study similar to a written consent. This procedure is valid according to the human research ordinance (HRO) Chapter 2 Article 9, when a study of risk category A with an adult capable of judgement and a disproportionate effort of providing a written informed consent is present. The ethics committee then has to be informed of this procedure and the burden of re-sending the written informed consent can so be reduced The Email can be found in Appendix 1. Patients will not receive any compensation for participating.

4.6 Study procedures

Upon return of written consent, patients receive an email with a link to the eCRF. This is composed in REDCap and contains a final check on the inclusion and exclusion criteria, the German version of the SIRSI, the German Version of the TSK-SI, the German Version of the WOSI, the SSV and sSSV, information on the RTS status and demographic and clinical information. If not completed reminders are sent every week for four times. Upon completion of the first round eCRF (T1) a second round eCRF (T2) is sent automatically after seven days containing another check on exclusion criteria and the German version of the SIRSI. If not completed three reminders are sent daily therefore a maximum time of ten days between measures (T1 and T2) is not exceeded. The duration to fill out the first round of questionnaires should take around 15 minutes and the second round around five minutes. The Data is stored within the REDCap database.

4.7 Withdrawal and discontinuation

The participation in the study is voluntary and all patients have the right to withdraw consent for participation in the study without prejudice. All data collected up to the time of

withdrawal will be used in the analysis as appropriate. Should a patient withdraw consent, he or she will be further treated and followed-up according to routine practice in the Schulthess Klinik Zürich. No further project-specific examinations or questionnaires will be performed. Patients are withdrawn from the study, if between T1 and T2 another instability event or other physical or psychological pathology that interferes with the RTS progress occurs. This information is asked for in the beginning of the second round in the eCRF. Lost to follow-up is defined as the subject does not complete questionnaires or follow-up visits but has not "officially" withdrawn from the project. To consider a subject lost to follow-up, the PI should make all reasonable efforts to locate and establish communication with the subject. All attempts should be documented within the source documents, indicating date, time, method, and site personnel. Withdrawal has no positive or negative consequences for the patient. In such cases, the clinical data already collected can continue to be used for regulatory and scientific evaluations.

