5.2 Statistical analysis plan

The reliability and validity of the German version of the Shoulder Instability-Return to Sport after Injury (SIRSI-D) and Tampa Scale of Kinesiophobia-Shoulder Instability (TSK-SI-D) score will be assessed through rigorous psychometric evaluation procedures.

Reliability will be evaluated to ensure the consistency and stability of the questionnaire over time.

Internal consistency, which measures the extent to which items within the questionnaire are correlated with one another, will be assessed using Cronbach's alpha coefficient. Test-retest reliability will be examined by administering the questionnaire to participants on two different timepoints one week apart and calculating the correlation between their scores.

Validity will be assessed to determine the extent to which the questionnaire measures the intended constructs of shoulder instability and return to sport after injury.

Content validity will be established by ensuring that the items in the questionnaire adequately cover all relevant aspects of the constructs.

Construct validity will be evaluated through factor analysis to confirm the underlying factor structure of the questionnaire and assess its convergent and divergent validity with other related measures.

Criterion validity will be examined through concurrent validity by comparing the scores of the SIRSI-D and TSK-SI-D questionnaire with SSV and WOSI.

Overall, these psychometric evaluation procedures will ensure that the German version of the SIRSI and TSK-SI-D scores are both reliable and valid for assessing shoulder instability and return to sport after injury in a German-speaking population. All statistical analyses are conducted in R (R Core Team (2022)).

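### The T2 form records nothing that identifies patients whose readiness really changed, so the SIRSI-D retest correlation cannot separate unequal real change from measurement error

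*Combined protocol and SAP*

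**What the plan says.** Section 4.7 sets the withdrawal rule for the retest interval: "Patients are withdrawn from the study, if between T1 and T2 another instability event or other physical or psychological pathology" interfering with progress towards sport occurs. It adds: "This information is asked for in the beginning of the second round in the eCRF".

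Section 4.6 describes T2 as "containing another check on exclusion criteria and the German version of the SIRSI". The measures that could show a change of status from outside the scale are listed for T1 only: the WOSI, "the SSV and sSSV, information on the RTS status and demographic and clinical information". T2 is sent seven days after T1 is completed, with three daily reminders so that "a maximum time of ten days between measures (T1 and T2) is not exceeded".

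Section 4.3 sets the phase of recovery: "Patients are excluded if they are not at least three months after the last instability event or a surgery for shoulder instability". Section 3.1 describes the target population as "treated conservatively or surgically and planning to return to sports".

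Section 5.2 plans test-retest reliability by giving the questionnaire "on two different timepoints one week apart and calculating the correlation between their scores". It does not say which correlation, defines no stable-patient analysis and plans no mean T1-T2 difference. ICC is in the glossary but is not named in 5.2. The TSK-SI is not listed in the T2 form, so what follows concerns the SIRSI-D.

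**The concern.** A test-retest coefficient measures the instrument only if the patients are the same at both times. The protocol accepts this, since it withdraws some patients who change, but the reasons in 4.7 are a new event or a new interfering pathology. A patient who goes back to training during the week passes every T2 check, and psychological readiness to return to sport is what the SIRSI measures (section 3.2). The T2 form has no item on perceived change, and RTS level is not asked again.

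If the coefficient comes out lower than hoped, the analyst will be unable to tell poor items from changed patients. If everyone moves up together, a correlation will not show it. Neither gap can be repaired once T2 has been collected.

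**Working it through.** **The plan's own figures.** No test-retest coefficient or retest sample size is stated, so there is none to reproduce. The figures in section 4.4 were checked because the SD comes from there.

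- Mean difference, SD 26.6, groups 71.83 and 45.25: half-width = t(0.975; 115 df) × 26.6 × √(1/71.83 + 1/45.25) = 1.981 × 5.048 = 10.0, a width of 20 as printed.
- Pearson 0.71, n = 99, Fisher z: 0.596 to 0.796, as printed.
- Final size: 117 × 1.15 = 134.55, rounded up to 135. With 15% lost, 135 × 0.85 = 114.75, so about 115 retest pairs.

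**Model.** T1 = t + e1 and T2 = t + d + e2, where t is true readiness, e1 and e2 are independent errors, and d is real change, independent of t, with mean μ and variance V(d).

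- Pearson = V(t) / √[V1 × V2], with V2 = V1 + V(d). The mean μ does not appear.
- Agreement ICC = 2V(t) / (V1 + V2 + μ²). Here both μ and V(d) count.

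**Inputs.** SD 26.6 (section 4.4), so V1 = 707.56. Reliability 0.90 is assumed, so V(t) = 636.80. If a share p improves by m on average with SD s, then μ = p·m and V(d) = p·s² + p(1−p)·m². The values of p, m and s are assumed; the documents give no expected change over 7 to 10 days.

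| Share improving | Mean (SD) of change | V(d) | V2 | Pearson | Agreement ICC |
|---|---|---|---|---|---|
| 10% | 10 (10) | 10 + 9 = 19 | 726.56 | 0.888 | 0.887 |
| 20% | 10 (10) | 20 + 16 = 36 | 743.56 | 0.878 | 0.875 |
| 20% | 15 (10) | 20 + 36 = 56 | 763.56 | 0.866 | 0.860 |

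Second row in full: 636.80 / √(707.56 × 743.56) = 636.80 / 725.34 = 0.878.

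**Other assumed reliabilities**, second row: 0.85 falls to 0.829, and 0.96 falls to 0.936.

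**Change shared by everyone.** If all patients improve by exactly 5 or 10 points, Pearson stays at 0.900. An agreement ICC would fall to 0.884 or 0.841.

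**Change affecting everyone unequally**, mean 0: Pearson falls to 0.885 if its SD is 5 and to 0.842 if its SD is 10. This is a harsher assumption than the table.

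**Sampling error for comparison.** With n = 115 and r = 0.90, Fisher z gives tanh(1.472 ± 1.96/√112), that is 0.858 to 0.930. Every row of the table lies inside this interval.

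**The case against.** The design already guards against change. The retest interval is short and capped, patients are at least three months past the event or surgery, and new events and pathologies are screened at T2. Even under the assumed scenarios the loss is within sampling error for about 115 pairs. Section 5.2 sets no reliability threshold, so no stated decision turns on it, and the effect on the coefficient is downward and therefore conservative. All of this stands, and it limits the point to a useful refinement.

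Three stronger readings are tempting, and the documents do not support them.

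- *Only patients who get worse are removed.* T2 rechecks the exclusion criteria, so someone who no longer aims to return to sport could also be removed. Gradual worsening without an event or new pathology stays in. What is missing is any marker of stability, in either direction.
- *All participants are by definition recovering.* Section 3.1 states an intention to return to sport, which does not establish measurable change within a week. Section 3.3 treats return to sport as a spectrum, so patients already partly back may be enrolled.
- *Recovery as such is counted as measurement error.* That would hold for an agreement ICC or a smallest detectable change. On the second row of the table, the latter would rise from 1.96 × √(2 × 70.76) = 23.3 to 1.96 × √(141.51 + 36 + 4) = 26.4 points. Section 5.2 names neither statistic. Under a Pearson correlation, only recovery that differs between patients has an effect.

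A fair objection also applies to the usual remedy. Choosing patients who say they are unchanged can select pairs that happen to differ little. In an illustrative worst case with no true change and reliability 0.90, perceived change was set to the observed score difference plus noise (SD 5 to 20), and pairs within 10 points were kept. The correlation in the kept pairs rose to between 0.97 and 0.92.

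**Conclusion.** The concern holds as a limited design gap. Nothing collected at T2 identifies SIRSI-D pairs in which readiness really changed for the better, or drifted without an event, and no stable-patient analysis is defined. Unequal real change therefore lowers the planned correlation and cannot be separated from measurement error afterwards, while a common shift would go unreported.

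The size is probably modest: from 0.90 to about 0.89 to 0.87 in the scenarios tabulated. This rests on the SD of 26.6 from section 4.4, an assumed reliability, assumed shares and sizes of change, and change that is unrelated to the true T1 level. Severity is low. It is worth acting on because the information is cheap to collect and cannot be recovered later.

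**What to change.** In section 4.6, add two short items to the T2 form:

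- the RTS-level question already used at T1;
- one single-topic item asking whether the shoulder is better, unchanged or worse than at the first questionnaire. It should not ask about confidence, which overlaps with what the SIRSI measures and would make the selection problem worse.

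In section 5.2, name the test-retest coefficient. Report it with its interval in all valid pairs and, beside it, in patients with unchanged RTS level and no reported change. Also report the mean T1-T2 difference with its interval, since the correlation cannot show a common shift.

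The cost is two items on a form expected to take about five minutes, plus one extra coefficient and one mean difference. The stable subset will be smaller, with a wider interval, and selecting on self-reported change may raise its reliability somewhat. For both reasons the full-sample result should stay alongside it.
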